## **Study purpose**

To evaluate the safety and preliminary efficacy of endovascular denervation (EDN) for the treatment of patients with peripheral artery disease (PAD).

## **Study design**

This study was a prospective, single-center, open-labeled, randomized controlled trial designed to evaluate the safety and efficacy of ER combined with EDN for treating lower limb PAD. Patients who meet the following criteria were randomly assigned to the group of ER alone or ER combined with EDN. Subjects in the control group were treated with ER including PTA, DCB, and/or stenting, and patients in the ER+EDN group were treated with EDN from distal iliac artery to proximal superficial femoral artery before ER.

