## **The exclusion criteria:**

- (a) thrombolytic therapy performed within 30 days;
- (b) patients who had undergone vascular bypass surgery before this study;
- (c) allergy or contraindication of antiplatelet drugs, anticoagulants, thrombolytic drugs and contrast agents,;
- (d) patients with obvious bleeding tendency, coagulation dysfunction, hypercoagulability and blood system diseases;
- (e) serious liver and kidney diseases;
- (f) history of hemorrhagic stroke within last month or ischemic stroke or transient ischemic attack within 2 weeks;
- (g) pacemaker implants;
- (h) patients who are pregnant, breast-feeding or planning pregnancy;
- (i) expected survival < 24 months.

**The primary endpoint** was the improvement of ABI at 6-month post-procedure.

**The secondary endpoints** included transcutaneous oxygen pressure (TcPO2), Rutherford category, numerical rating scale (NRS) score and safety.

**Safety endpoints** was the occurrence of trial-related adverse events that occurred during this trial. Possible adverse or serious adverse events during surgery: femoral artery stenosis, femoral artery dissection, thromboembolism (stroke or TIA), pus, hematoma at the puncture site, arteriovenous fistula requiring blood transfusion and/or surgical treatment, and other "serious" adverse events during the trial.

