### **Visit 2 (0 day, Baseline):**

The visit was considered to determine the patient's admission/procedure date. For patients meeting the requirements, balloon catheter pre-dilation after DSA of the artery at the affected site, femoral popliteal artery stent implantation, balloon catheter post-dilation, and then arterial and nerve radiofrequency ablation were performed.

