#### **Visit 6 (6 months±7 days):**

The visit was considered 6 months ±7 days after surgery. Blood routine examination, renal function, liver function, coagulation function, blood lipid, blood electrolyte, catecholamine, glycosylated hemoglobin, angiotensin II, aldosterone, insulin, glucagon, homocysteine, blood pressure assessment, blood glucose, ankle-brachial index (ABI), transcutaneous partial pressure of oxygen (TcPO2), foot sensory threshold measurement, VUS microcirculation detection, blood pressure assessment, blood pressure assessment, blood pressure assessment. Rutherford scale, Wagner scale of diabetic foot ulcer, pain NRS score, painless walking distance PFWD examination, color Doppler ultrasound, computed tomography angiography (CTA), drug use and complications.

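### Open-label design leaves the self-rated pain NRS, and in part Rutherford category, mixing patient expectation with EDN; participant masking is worth specifying and may need no separate sham

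*Combined protocol and SAP*

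**What the plan says.** Study design calls the trial a "prospective, single-center, open-labeled, randomized controlled trial", with patients "randomly assigned to the group of ER alone or ER combined with EDN". No section describes masking of patients or assessors, and none gives a reason for leaving it out.

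Both arms undergo a catheter procedure. On the control arm: "Subjects in the control group were treated with ER including PTA, DCB, and/or stenting". On the experimental arm: "patients in the ER+EDN group were treated with EDN from distal iliac artery to proximal superficial femoral artery before ER". The Visit 2 section gives a different order, with ablation last: "balloon catheter post-dilation, and then arterial and nerve radiofrequency ablation were performed".

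The endpoint paragraphs, printed under the exclusion criteria heading, say that the primary endpoint "was the improvement of ABI at 6-month post-procedure". They list TcPO2, Rutherford category, NRS score and safety as secondary. NRS is collected at Visits 1, 3, 4, 5 and 6, and Rutherford category at Visits 1, 4, 5 and 6. Pain-free walking distance is also measured (at Visit 6 the list includes "pain NRS score, painless walking distance PFWD examination"), but it is not named as an endpoint.

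Statistics and Analysis compares the groups by Student's t-test, Mann-Whitney or chi-square, with significance at P < 0.05.

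**The concern.** An NRS score is the patient's own judgement of pain. If patients know whether they received an additional procedure meant to help their disease, that knowledge can move the score whether or not EDN works. Masking the person who writes the score down does not remove this; only keeping the patient unaware does. The same applies, in part, to Rutherford category, to the extent that it depends on symptoms the patient reports.

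The study purpose is to assess safety and preliminary efficacy. A lower NRS in the EDN arm could be read as a symptom signal and carried into a later trial, yet under this design it could not be attributed to EDN alone. The comparator makes this worth raising: controls already have an invasive catheter procedure, so the familiar objection that they would need a separate invasive sham may not apply.

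**Working it through.** **Which endpoints are exposed**

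- NRS (secondary): rated by the patient; fully exposed.
- Rutherford category (secondary): rests partly on reported symptoms; partly exposed.
- ABI (primary) and TcPO2 (secondary): instrument measurements; much less affected by what the patient knows. Whether the person measuring ABI should be masked is a separate question.
- Pain-free walking distance: ends when the patient reports pain, so it is exposed, but it is not a listed endpoint.

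**What bears on feasibility**

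- Stated: both arms have ER, EDN is added to it, and Visit 2 lists ablation together with angiography, dilation and stenting.
- Not stated: sedation or anaesthesia, whether ablation can be felt, added procedure time, access site in either arm, and who collects NRS.
- Inconsistent: Study design puts EDN before ER, while Visit 2 puts ablation after stenting and post-dilation. The order may affect what a patient could notice.

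**Illustration of size**

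The plan has no figure to reproduce here. The sample size is given as 20, with no effect size, SD, power or dropout, and no size for an expectation effect appears anywhere.

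From the plan: total N = 20; significance level 0.05; two-group t-test. Assumed: 1:1 allocation (10 per arm), a two-sided test, NRS SD of 2, no true EDN effect on NRS, and an expectation shift *b* of 0.5, 1.0 or 1.5 points in favour of EDN.

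1. Standard error of the difference: SD × √(2/n) = 2 × √(2/10) = 0.894 points.
2. Degrees of freedom: 10 + 10 − 2 = 18; two-sided 5% critical value t = 2.101.
3. Noncentrality: λ = b / 0.894.
4. Rejection rate: P(|T| > 2.101), where T is noncentral t with 18 df and noncentrality λ.

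| Shift b (points) | b in SD | λ | Rejection rate |
|---|---|---|---|
| 0 | 0 | 0 | 5.0% |
| 0.5 | 0.25 | 0.559 | 8.3% |
| 1.0 | 0.50 | 1.118 | 18.5% |
| 1.5 | 0.75 | 1.677 | 35.5% |

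A simulation of 100,000 trials at each shift gave 4.9%, 8.3%, 18.6% and 35.5%, in agreement.

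Put another way, if the observed SD is 2, a difference must reach 2.101 × 0.894 = 1.88 points to be significant. A shift of 0.5 to 1.5 points supplies 0.5/1.88 = 27% to 1.5/1.88 = 80% of that before EDN contributes anything.

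Masking does not alter the sample size. If it removed the shift entirely, the rejection rate would return to 5%.

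**The case against.** The strongest reply is that this is a 20-patient preliminary study whose primary endpoint is not self-reported. The exposed endpoints are secondary, and the percentages come from feeding a chosen bias into a t-test. Nothing in the documents shows that an expectation effect of any size would last to six months. All of this stands. It limits the point to the symptom endpoints and makes the figures an illustration rather than evidence of how large the bias is.

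A second reply concerns feasibility. A reader might infer from the shared catheter procedure that masking is easy and needs neither a sham nor extra staff. The documents do not support that. EDN is described as radiofrequency ablation, and nothing shows that an awake control patient could not tell it was omitted. If the step is perceptible, some mimicking of it might be needed. That both arms share the same access route is also not stated. Nor is masking free of effort: staff at a single centre who know the arm would have to avoid revealing it from Visit 2 to Visit 6, including while recording the relationship of adverse events to the device. This also stands. It does not defeat the proposal, because imperfect masking still reduces the bias compared with open disclosure.

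A third reply is that no section says in words that patients are told their arm. That is true: disclosure is inferred from the open-label description. It is the ordinary meaning of the term, and nothing in the protocol contradicts it.

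**Conclusion.** The concern holds for NRS and, in part, for Rutherford category. Under the plan as written, a between-arm difference in these endpoints cannot be separated from patient expectation, and no safeguard is described. A reader might go further and conclude that the trial's efficacy claim as a whole is uninterpretable. The documents do not support that, since ABI and TcPO2 are instrument measurements and much less affected by what the patient knows.

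The size is unknown. With 10 per arm, SD 2, a two-sided test and a pure expectation shift of 0.5 to 1.5 points, all assumed, false-positive NRS results would occur in about 8% to 36% of trials instead of 5%. The recommendation does not depend on those figures. It rests on the open-label design, the self-rated endpoint, and a remedy that is cheap and may need no separate sham.

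**What to change.** 1. In Study design, replace open-label with participant-masked. State that the arm is not disclosed to the patient until the Visit 6 assessments are complete, with disclosure at any time if needed for safety.
2. Say in the consent form that EDN may or may not be added to the procedure.
3. Instruct staff who know the arm not to reveal it, and state who collects NRS.
4. At Visit 6, before disclosure, ask each patient which arm they believe they had, and report the answers by arm.
5. State the sedation used and whether the ablation is expected to be felt, so that a reader can judge whether masking is realistic. Reconcile the order of EDN and ER between Study design and Visit 2.
6. If masking is judged infeasible, say why, and label the between-arm comparisons of NRS and Rutherford category as exploratory and open to expectation bias. Walking distance needs no relabelling as an endpoint because it is not listed as one; if it is reported by arm, the same caveat applies.

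The cost is protocol and consent wording, one question at Visit 6, and staff discipline over six months; no patients are added. Masking will be imperfect, because some patients may guess from the length or feel of the procedure. The belief question helps to show how far that happened, although a patient who improves may guess EDN for that reason alone. The fallback in item 6 costs a sentence or two.

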## **Sample size**

1 site, 20 subjects.

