## **The inclusion criteria:**

- (a) eligible subjects aged 18-75 years;
- (b) clinically confirmed PAD in the lower extremities;
- (c) Rutherford category II-VI.

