## **Statistics and Analysis**

All continuous data are presented as mean  $\pm$  standard deviation (SD) or median with interquartile range. Categorical data are reported as numbers and percentages. Paired *t*-test and Wilcoxon signed-rank test were used to compare parameters at baseline and the 6-month follow-up. Student's *t*-test and Mann-Whitney *U* test were used to compare parameters between the two groups. When multiple follow-ups were analyzed, one-way repeated-measures ANOVA along with Bonferroni correction were used. Differences in categorical data between the two groups were analyzed using the chi-square test. *P* < 0.05 was considered statistically significant. All statistical analyses were performed using SPSS (version 22.0, SPSS, Chicago, USA) and GraphPad Prism 8 (GraphPad Software, San Diego, California).

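### Rutherford II-VI patients are compared in a 20-patient trial with no severity adjustment and no described stratification, so a chance severity imbalance would go uncorrected and power is lost if severity is prognostic

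*Combined protocol and SAP*

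**What the plan says.** Under Study design the trial is a "prospective, single-center, open-labeled, randomized controlled trial", and the only statement on allocation is "Patients who meet the following criteria were randomly assigned to the group of ER alone or ER combined with EDN". No ratio, sequence generation, blocking, stratification, minimisation or concealment is described anywhere.

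The inclusion criteria admit "Rutherford category II-VI", which is five categories. The Sample size section reads "1 site, 20 subjects", with no effect size, SD or power.

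The endpoint paragraphs, which follow the exclusion criteria, say that the primary endpoint "was the improvement of ABI at 6-month post-procedure". TcPO2 is a secondary endpoint, along with "Rutherford category, numerical rating scale (NRS) score and safety". Rutherford category is thus both an entry criterion and an outcome. It is recorded at Visit 1, before the procedure.

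Under Statistics and Analysis, the Student's t and Mann-Whitney U "test were used to compare parameters between the two groups", and categorical data go to a chi-square test. The repeated-measures ANOVA is one-way. None of these is given a baseline or severity term.

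**The concern.** Three features occur together: a wide entry range on a severity scale, a very small sample, and neither balancing nor adjustment for severity in the text. With 20 patients, random assignment often leaves the arms visibly different in severity. If severity is related to 6-month change, two things follow.

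- **In the individual trial:** an unlucky draw moves the estimated EDN effect up or down, and the planned tests have no means of correcting it.
- **On average:** variation between severity groups stays in the error term, so the comparison is less precise than the data already collected would allow.

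The link is most direct for Rutherford category, where the starting category limits how far a patient can improve. For ABI change the documents give no figure, so the size of the problem there has to be shown over a range.

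**Working it through.** **Inputs from the documents:** 20 patients; Rutherford II-VI; unadjusted between-arm tests; significance at P < 0.05 (taken as two-sided). The plan gives no derivation of 20, so there is no figure of its own to reproduce. For scale, 10 per arm gives 80% power in a t-test only for a difference of about 1.32 SD.

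**Assumptions:** two severity strata (II-III and IV-VI); 4 to 10 of 20 patients in the severe stratum; severity shifts the outcome by 1.0 or 1.5 within-stratum SD; true effect 0 or 1.25 SD; 10:10 arms unless stated.

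**Step 1. How often severity is unbalanced.** At 10:10, the number of severe patients in one arm is hypergeometric, with C(20,10) = 184,756 allocations.

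- 10 severe, split 7:3 or worse: 2 × (1 + 100 + 2,025 + 14,400) / 184,756 = 2 × 16,526 / 184,756 = 17.9%.
- 6 severe, split 5:1 or worse: 2 × (1,001 + 6 × 2,002) / 184,756 = 2 × 13,013 / 184,756 = 14.1%.
- 4 severe, split 4:0: 2 × 8,008 / 184,756 = 8.7%.

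Each of these is a gap of at least 40 percentage points. A gap of at least 20 points has probability 58% (4 severe) to 66% (10 severe).

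Under simple, unblocked randomisation the 40-point gap is rarer: 8.6% with 6 severe and 12.4% with 10. Gaps of exactly 40 points are common at 10:10, which accounts for part of the difference. Arm size is a separate matter. With simple randomisation, exactly 10:10 occurs 17.6% of the time and 13:7 or worse 26.3%.

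**Step 2. What a 7:3 split does (10 severe).** Expected spurious difference = (0.7 − 0.3) × shift, which is 0.4 SD at shift 1.0 and 0.6 SD at shift 1.5. In simulation with no true effect, the unadjusted t-test rejects in about 9-10% (shift 1.0) or 13% (shift 1.5) of trials with that split. In trials with 5 severe patients in each arm it rejects in only 2.8% or 1.3%. Averaged over all allocations the rate is 5.0%.

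With a true effect of 1.25 SD, the unfavourable 7:3 split leaves power of 36% (shift 1.0) or 15% (shift 1.5). The favourable split gives 90% or 92%.

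**Step 3. Precision.** For the unadjusted difference, variance = (1/10 + 1/10) × (1 + shift² × 0.263), where 0.263 = 10 × 10 / (20 × 19) is the variance of the severity indicator.

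- Shift 1.0: √(0.2 × 1.263) = 0.50.
- Shift 1.5: √(0.2 × 1.592) = 0.56.
- Severity balanced and in the model: √0.2 = 0.45.

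The simulated SDs agree (0.50, 0.56-0.57 and about 0.45).

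**Step 4. Power at a true effect of 1.25 SD, 10 severe of 20 (simulation).**

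| Allocation and analysis | Shift 1.0 SD | Shift 1.5 SD |
|---|---|---|
| Unstratified, unadjusted (as planned) | 65% | 55% |
| Stratified, unadjusted | 67% | 56% |
| Unstratified, severity term | 73% | 73% |
| Stratified, severity term | 75% | 75-76% |

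Repeat simulations put the third row at 72-74%. Nearly all the gain comes from the model term; stratification adds about 1-3 points.

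**Step 5. Price if severity is not prognostic.** Power with the severity term does not depend on the shift, so it is also about 73% at shift 0. The unadjusted t-test there has 75.3%. One unneeded term therefore costs about 2 points. A baseline covariate takes one more degree of freedom (18 to 17 with severity, 16 with both). The simulation did not include that covariate.

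**The case against.** **Silence is not a method.** A reader might infer that the trial was randomised without stratification. The documents do not say so; they describe no method at all. What stands is that none is described, and that the stated analysis would not use a stratum even if there were one.

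**The test is valid.** A reader might also infer that the plan inflates false positives. It does not: random allocation already allows for chance imbalance, and the average type I error is about 5%. The 9-13% in Step 2 applies only to trials that drew a 7:3 split, and it is offset by rates below 5% in balanced trials. What remains is an estimate that is hard to interpret after an unlucky draw, and lost power.

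**It can be repaired in analysis.** It is tempting to say that 20 patients are too few to correct an imbalance afterwards. Step 4 shows otherwise under the stated assumptions, which is why the main change belongs in the analysis and not in the allocation.

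**The primary endpoint is an improvement.** If computed as a change, it takes some account of baseline ABI. That is fair, but it does not adjust for Rutherford category.

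**The effect of severity is assumed.** The documents give no relation between Rutherford category and ABI change, and they do not say whether NRS measures pain at rest or on walking. Nor do they show that Rutherford category is a better factor than baseline ABI or type of ER. These objections stand. They are why the result is conditional and why baseline ABI also belongs in the model.

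**The aim is preliminary.** The stated purpose covers safety and early efficacy, which lowers the stakes. The plan nevertheless tests between arms at P < 0.05.

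**Conclusion.** The point holds as a matter of precision and of protection for the single trial being run, not as a matter of validity. The plan combines Rutherford II-VI entry, 20 patients, no described stratification or blocking, and unadjusted between-arm tests.

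If severity shifts the outcome by 1.0 to 1.5 SD, 10 of 20 patients are severe, arms are 10:10 and the true effect is 1.25 SD, adding a severity term raises power from about 55-65% to about 72-74%. Stratifying as well brings it to about 75%. If severity is unrelated to the outcome there is no gain, and the term costs a few power points. Because the severity data are already collected and the cost is small, the change is worth making.

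**What to change.** **Main change, in Statistics and Analysis.** Replace the unadjusted between-arm tests of the continuous 6-month endpoints (ABI, TcPO2, NRS) with a linear model (ANCOVA) containing treatment arm, the baseline value of the endpoint, and Visit 1 Rutherford category as II-III versus IV-VI. Report the adjusted difference with its confidence interval. Two levels are workable with 20 patients; five would be too sparse. Rutherford category as an outcome is ordinal and is not covered by this model. The text is in the past tense: if allocation is complete, the model can still be adopted, but it should be dated before the arms are compared, or else labelled post hoc. Cost: one or two degrees of freedom, and a few power points if severity is not prognostic. No added patients, visits or measurements.

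**Optional and secondary, in Study design, only if allocation has not begun.** State 1:1 randomisation stratified by the same two-level factor, with concealed permuted blocks of varying size. The costs are slight predictability in an open-label single-centre trial and possibly small inequality of arm sizes from unfinished blocks. Pair it with the stratum term: in trials balanced on severity, the unadjusted test has a type I error of only 1.3-2.8% under the same assumptions, so it would be conservative.

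If allocation has already taken place, the Study design section should state the method that was used.

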## **Sample size**

1 site, 20 subjects.

## **The inclusion criteria:**

- (a) eligible subjects aged 18-75 years;
- (b) clinically confirmed PAD in the lower extremities;
- (c) Rutherford category II-VI.

## **The exclusion criteria:**

- (a) thrombolytic therapy performed within 30 days;
- (b) patients who had undergone vascular bypass surgery before this study;
- (c) allergy or contraindication of antiplatelet drugs, anticoagulants, thrombolytic drugs and contrast agents,;
- (d) patients with obvious bleeding tendency, coagulation dysfunction, hypercoagulability and blood system diseases;
- (e) serious liver and kidney diseases;
- (f) history of hemorrhagic stroke within last month or ischemic stroke or transient ischemic attack within 2 weeks;
- (g) pacemaker implants;
- (h) patients who are pregnant, breast-feeding or planning pregnancy;
- (i) expected survival < 24 months.

**The primary endpoint** was the improvement of ABI at 6-month post-procedure.

**The secondary endpoints** included transcutaneous oxygen pressure (TcPO2), Rutherford category, numerical rating scale (NRS) score and safety.

**Safety endpoints** was the occurrence of trial-related adverse events that occurred during this trial. Possible adverse or serious adverse events during surgery: femoral artery stenosis, femoral artery dissection, thromboembolism (stroke or TIA), pus, hematoma at the puncture site, arteriovenous fistula requiring blood transfusion and/or surgical treatment, and other "serious" adverse events during the trial.

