#### **Adverse event observation**

All adverse events were observed, and detailed description of symptoms, date of occurrence, date of termination, relationship between degree and device, course of

treatment, and outcome were recorded. If fatal, disabling, teratogenic and other serious adverse events occur, regardless of whether they are related to the trial, emergency measures should be taken immediately to protect the interests of patients, and the main research unit, the ethics committee, the sponsor and the State Food and Drug Administration should be reported within 24 hours after being informed.

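### The safety endpoint counts only trial-related adverse events in an open-label trial with no masked causality assessment described, so the between-arm comparison is open to differential attribution

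*Combined protocol and SAP*

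**What the plan says.** - **Endpoint.** The Safety endpoints paragraph, which sits under the exclusion criteria heading, says the endpoint "was the occurrence of trial-related adverse events that occurred during this trial". It does not define *trial-related*: the term could refer to EDN, to endovascular revascularisation (ER) or to any trial procedure.
- **Event list.** The next sentence lists possible events during surgery and closes with "and other 'serious' adverse events during the trial". No relatedness condition is attached to that last item, and it is unclear whether the list is part of the endpoint.
- **Design.** The Study design section describes a "prospective, single-center, open-labeled, randomized controlled trial". Both arms receive ER; "patients in the ER+EDN group were treated with EDN from distal iliac artery to proximal superficial femoral artery before ER".
- **Collection.** The Adverse event observation section states: "All adverse events were observed, and detailed description of symptoms, date of occurrence, date of termination, relationship between degree and device". Serious events are to be reported "regardless of whether they are related to the trial", but that is a rule for expedited reporting and does not define the endpoint.
- **Role and analysis.** The Study purpose section begins "To evaluate the safety and preliminary efficacy of endovascular denervation (EDN", and safety is listed as a secondary endpoint. The Statistics and Analysis section gives a general rule: "Differences in categorical data between the two groups were analyzed using the chi-square test".
- **Not described.** There is no named relatedness assessor, causality scale, masked assessment or events committee, and no between-arm analysis of events from all causes.

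**The concern.** Randomised arms can be compared on all adverse events without anyone judging cause. A relatedness filter adds a judgement between the event and the count, and here nothing in the plan keeps that judgement from being made with knowledge of the arm. Events after the new procedure may be attributed to it too readily, or put down to ER or to the underlying arterial disease. ER is trial treatment in both arms, so ER events can qualify in either arm. The risk is that similar events are classified differently by arm.

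The item recorded on causality is relationship to the *device*, whereas the endpoint filter is relationship to the *trial*. If the device is the EDN device, the item has no counterpart in the ER-alone arm. The plan does not say.

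At stake is the safety half of the study purpose. Differential attribution could create, reverse or hide a difference, and a reader of the results could not tell which had happened.

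**Working it through.** The plan gives no event rate, attribution rate or safety target, so there is no figure of its own to reproduce. What follows is illustrative.

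**Inputs**
- From the plan: 20 subjects (Sample size); chi-square for categorical data and significance at P < 0.05 (Statistics and Analysis).
- Assumed: 10 patients per arm, since the allocation ratio is not stated; the event rates *p*; and the attribution shares *a*, meaning the probability that a patient with an event is counted as having a related one.

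**Formula.** Displayed rate in an arm = *p* × *a*. If *p* is the same in both arms, displayed difference = *p* × (*a*_EDN − *a*_ER).

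**Equal true rates of 30%**
- Attribution 90% v 50%: 0.30 × 0.90 = 27% and 0.30 × 0.50 = 15%, a difference of +12 points.
- Attribution 50% v 90%: 15% v 27%, or −12 points.
- Attribution 70% v 70%: 0.30 × 0.70 = 21% in both arms, difference 0. The filter biases the difference under equal true rates only when attribution differs by arm.

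**Range.** For *p* of 10–40% and an attribution gap of 10–40 points, the shift runs from 0.10 × 0.10 = 1 point to 0.40 × 0.40 = 16 points, in either direction.

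**Masking.** With true rates of 40% (ER+EDN) v 20% (ER) and attribution of 50% v 90%, the displayed rates are 0.40 × 0.50 = 20% and 0.20 × 0.90 = 18%. A true excess of 20 points appears as 2.

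**Effect on the test.** For each scenario the rejection probability is the sum, over all pairs of counts (*x*, *y*) from 0 to 10, of Bin(*x*; 10, displayed EDN rate) × Bin(*y*; 10, displayed ER rate), taken where the two-sided P is below 0.05. The chi-square is the uncorrected Pearson test; Fisher's exact test is shown for comparison.

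| True rate, both arms | Attribution, ER+EDN v ER | Displayed rates | Chi-square rejects | Fisher rejects |
|---|---|---|---|---|
| 30% | no filter | 30% v 30% | 3.7% | 1.2% |
| 30% | 90% v 50% | 27% v 15% | 6.8% | 2.3% |
| 20% | 80% v 40% | 16% v 8% | 2.8% | 0.6% |
| 40% | 80% v 40% | 32% v 16% | 9.8% | 3.9% |
| 60% | 80% v 40% | 48% v 24% | 17.0% | 8.0% |

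**A single table.** Suppose 4/10 v 4/10 patients have an event from any cause (P = 1.0). If every control event is judged unrelated, the endpoint reads 4/10 v 0/10. Chi-square = 20 × (4×10 − 6×0)² / (4 × 16 × 10 × 10) = 32,000 / 6,400 = 5.0, P = 0.025; Fisher P = 0.087. This is an extreme case, but it shows how few attribution decisions can change the safety result.

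**The case against.** The strongest reply has five parts.

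- **The restriction is not certain.** The event list ends with serious events that carry no relatedness condition. This stands as an ambiguity. But the list is introduced as possible events during surgery, so it does not clearly lift the filter. At best, serious events escape it and non-serious ones do not.
- **The listed events leave little room for judgement.** Dissection, puncture-site haematoma or arteriovenous fistula would probably be called related in either arm. This is fair: the problem bears more on later, non-specific events, and one attribution share for all events is a simplification.
- **The sizes are assumed and small against the noise.** At 27% v 15% with 10 per arm, the standard error of the difference is √(0.27×0.73/10 + 0.15×0.85/10) = √0.0325, about 18 points. A 12-point shift is less than one standard error. Even the unfiltered 40% v 20% comparison would reject in only about 13% of trials. This also stands, and the comparison is essentially descriptive. The displayed proportions are then the main safety output, and those are what the filter distorts.
- **No safety test is named, and all events are recorded anyway.** The chi-square rule is generic, so its use for safety is an inference, though a reasonable one for a secondary endpoint. All-cause counts can be recovered from the data. That makes the remedy cheap but does not make all-cause counts the planned comparison.
- **The device wording is visibly garbled.** It should carry little weight, and the point does not depend on it.

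**Conclusion.** The concern holds. As written, the endpoint makes the between-arm safety comparison depend on a causality judgement that is undefined and, as far as the documents show, unmasked. Neither the size nor the direction of any bias can be established from the documents. Under the assumed rates and gaps it is 1 to 16 points either way, and in the masking example a 20-point excess falls to 2. The effect is mainly on the estimate: at an assumed 10 per arm, false rejection rises from 3.7% (30% v 30%, unfiltered) to 6.8% (27% v 15%), and by more only under higher event rates. No figure in the plan is shown to be wrong. This is a change that should be made because it removes an avoidable source of bias at little cost. Confidence is medium, because the impact rests on assumption and the scope of the event list is unclear.

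**What to change.** 1. Define the main safety comparison as the number of patients with any adverse event, and separately with any serious adverse event, from the procedure to 6 months, by randomised arm and regardless of attribution.
2. Report exact 95% confidence intervals for each arm's proportion and for the difference.
3. Keep relatedness as a descriptive column. State what it refers to (EDN, ER or another trial procedure), the scale and the assessor, and use the same term in the endpoint and in the adverse event record.
4. State whether the list of possible events, including the closing item on serious events, is part of the endpoint.

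The cost is wording and tabulation. The Adverse event observation section already provides for recording all events, and Visits 3 to 6 record complications up to 6 months, so no new data are needed. One small downside is that more background events will be counted in both arms, which may dilute a procedure-specific signal; the relatedness column helps with that. The change does not remove open-label differences in how events are detected or reported.
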